11.3.7. Safety Scales

11.3.7.1. Electronic Columbia-Suicide Severity Rating Scale

The Columbia-Suicide Severity Rating Scale (C-SSRS) is a tool designed to systematically assess and track suicidal AEs (suicidal behavior and suicidal ideation). The electronic Columbia-Suicide Severity Rating Scale (eC-SSRS) is a computer-automated, subject-reported version of the C-SSRS, in which the subject's response to a question prompts and shows the appropriate follow-up questions (if any).

The strength of this suicide classification system is in its ability to comprehensively identify suicidal events while limiting the over-identification of suicidal behavior. The eC-SSRS scale takes approximately 5 minutes to administer. Occurrence of suicidal ideation is defined as having answered "yes" to at least one of the 5 suicidal ideation sub-categories (wish to be dead, non-specific active suicidal thoughts, active suicidal ideation with any methods [not plan] without intent to act, active suicidal ideation with some intent to act [without specific plan], and active suicidal ideation with specific plan and intent) at any evaluation. Occurrence of suicidal behavior is defined as having answered "yes" to at least one of the 4 suicidal behavior sub-categories (actual attempt, interrupted attempt, aborted attempt, and preparatory acts or behavior) at any post-baseline evaluation.

The "Baseline/Screening" (lifetime) version should be administered at the screening visit and the "Since Last Visit" version at all other time points.

Subjects who express suicidal ideation or behavior in completion of the eC-SSRS during the course of the study should be evaluated by the investigator and referred to a mental health professional at the discretion of the investigator.

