2.4.4. Safety Endpoints

- Number and percentage of subjects with AEs.
- Number and percentage of subjects with serious adverse events (SAEs).
- Number and percentage of subjects with AEs leading to discontinuation.
- Electronic Columbia-Suicide Severity Rating Scale (eC-SSRS): Proportion (%) of events in each classification class (as completed by the subject).
- Changes from baseline in clinical laboratory parameters, including thyroid panel.
- Changes from baseline in vital signs parameters.
- Score of AED-specific AEs (by the Liverpool Adverse Event Profile [LAEP]).

2.4.5. **Exploratory Endpoints**

- Seizure data recorded by an investigational wearable watch device from Empatica.
- Seizure data recorded by an investigational electronic seizure diary from Empatica MATE application.

3. Study Design

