16.6. Other Safety Assessments

16.6.1. Electronic Columbia Suicide Severity Rating Scale (eC-SSRS)

The eC-SSRS is a tool designed to systematically assess and track suicidal behavior and suicidal ideation for life time prior to the screening visit, and throughout the study. The strength of this suicide classification system is in its ability to comprehensively identify suicidal events while limiting the over-identification of suicidal behavior. The eC-SSRS Baseline/Screening Version is used at the screening visit and the eC-SSRS Since Last Visit Version is used from Visit 2 onward.

Subjects with complete and incomplete eC-SSRS records in the same visit, both records will be included in the listing.

Subjects who have complete and incomplete eC-SSRS records in the same visit, only complete records will be included in the summary tables. otherwise the incomplete record will be included in the tables.

eC-SSRS includes four sections: Suicidal Ideation, Intensity of Ideation, Suicidal Behavior, and Answer for Actual Suicide Attempts.

The following outcomes are eC-SSRS categories and have binary responses (yes/no). The categories are re-ordered from the scale to facilitate the definitions of the eC-SSRS endpoints, and to provide clarity in the presentation of the results.

Suicidal ideation is measured by 5 categories, representing 5 subtypes of suicidal ideation with increasing severity:

1. Category 1: Wish to be Dead
2. Category 2: Non-specific Active Suicidal Thoughts
3. Category 3: Active Suicidal Ideation with Any Methods (Not Plan) without Intent to Act
4. Category 4: Active Suicidal Ideation with Some Intent to Act, without Specific Plan
5. Category 5: Active Suicidal Ideation with Specific Plan and Intent

Suicidal behavior is measured by 5 categories, representing 5 subtypes of suicidal behavior:

1. Category 6: Preparatory Acts or Behavior
2. Category 7: Aborted Attempt
3. Category 8: Interrupted Attempt
4. Category 9: Actual Attempt (non-fatal)
5. Category 10: Completed Suicide

The 10 categories above are not mutually exclusive. Subjects will be counted in each category for which they have an event.

Self-injurious behavior without suicidal intent is a non-suicide-related eC-SSRS outcome, and has a binary response (yes/no).

For eC-SSRS analysis, “baseline” and “post-baseline” are defined as follows.

Time point	Study Visit	eC-SSRS Version	Derivation Rule

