Baseline	Screening/Visit 1	Baseline/Screening – life time, past one months and past two years	Most severe outcome
	Titration/Visit 2	Since Last Visit	

Post-baseline	All post-baseline visits up to and including Week 27/Visit 9, including unscheduled visits	Since Last Visit	Most severe outcome
---------------	--	------------------	---------------------

eC-SSRS composite endpoints will be derived for each time point of interest (i.e. baseline, post baseline, and each study visit) as follows:

Any suicidal ideation: A “yes” answer to any one of the 5 suicidal ideation questions on eC-SSRS (Categories 1-5).

Any suicidal behavior: A “yes” answer to any one of the 5 suicidal behavior questions on the eC-SSRS (Categories 6-10).

Any suicidality: A “yes” answer to any one of the 10-suicidal ideation and behavior questions on the eC-SSRS (Categories 1-10).

For each subject, the suicidal ideation score at each time point of interest (i.e. baseline, post baseline, and each study visit) is defined as the maximum suicidal ideation category (1-5) present for the time of interest. If no ideation is present a score of 0 is assigned. A suicidal ideation score of 4 or 5 is considered serious.

The number and percentage of subjects with any suicidality, any suicidal ideation and subtypes of ideation, any suicidal behavior and subtypes of behavior, and any non-suicidal self-injurious behavior will be presented for:

- Baseline (as defined above)
- Post-baseline (as defined above)
- Each scheduled study visit: Screening (lifetime), Titration/Visit 2, Week 3/Visit 3, Week 7/Visit 4, Week 11/Visit 5, Week 15/Visit 6, Week 19/Visit 7, Week 23/Visit 8, Week 27/Visit 9, EDV.

Shift in suicidal ideation score from baseline to the post-baseline time point and to each the following study visit will be presented: Week 3/Visit 3, Week 7/Visit 4, Week 11/Visit 5, Week 15/Visit 6, Week 19/Visit 7, Week 23/Visit 8, Week 27/Visit 9, EDV.

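### SAP 16.6.1 counts completed suicide through an answer on a form the subject completes, so that row can only read zero

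*SAP*

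**What the plan says.** Both documents treat the eC-SSRS as self-report. Protocol 11.3.7.1 says it "is a computer-automated, subject-reported version of the C-SSRS", and the safety endpoint in SAP 2.4.4 is "Proportion (%) of events in each classification class (as completed by the subject").

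The protocol defines suicidal behavior as a yes to "at least one of the 4 suicidal behavior sub-categories": actual, interrupted and aborted attempts, and preparatory acts.

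SAP 16.6.1 uses ten categories, which it introduces with "The following outcomes are eC-SSRS categories and have binary responses (yes/no"). Five concern ideation and five behavior; the fifth behavior category is "Category 10: Completed Suicide". Two composites follow. Any suicidal behavior is a yes "answer to any one of the 5 suicidal behavior questions on the eC-SSRS (Categories 6-10"). Any suicidality is a yes "answer to any one of the 10-suicidal ideation and behavior questions on the eC-SSRS (Categories 1-10"). The SAP commits to counts and percentages for both composites and for every behavior subtype, at baseline, post-baseline overall and by visit.

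SAP 3.4.2, which records changes from the protocol's planned analyses, does not mention the added category.

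**The concern.** A subject who has died by suicide cannot answer a later form. If a yes answer is the only route into Category 10, the report will carry a completed-suicide row that reads zero whatever happens in the trial. A reader would take that zero as something observed, although it follows from the derivation. If a suicide did occur, the summary of AEs leading to death would show it while the suicidality table showed none, and the composites could leave out the most severe outcome they are meant to contain. The eC-SSRS is a named safety endpoint in both documents, so its table will be read on its own.

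**Working it through.** The plan states no figure to reproduce here. The check is mainly a reading of the derivation, with a small calculation for scale.

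**Step 1: can Category 10 be filled?** It needs a yes from the subject on a form completed after the event. That is impossible, so its count is 0 for any true number of suicides.

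**Step 2: what reaches the composites?** With Category 10 empty, any suicidal behavior (Categories 6-10) reduces to Categories 6-9, and any suicidality (1-10) reduces to 1-9. A subject who dies by suicide is therefore counted post-baseline only after an earlier post-baseline yes:
- to an item in Categories 6-9, for any suicidal behavior;
- to an item in Categories 1-9, for any suicidality.

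**Step 3: does any other text supply a source?**
- SAP 16.6.1 says subjects are counted in each category where they have an event. It names no source other than the form, and the composite definitions require an answer.
- SAP 16.6.1 describes an actual-lethality rating whose top level is death. That rating goes to data listings and feeds neither Category 10 nor the composites.
- SAP 7.2 plans no imputation for safety measures.
- SAP 9 (disposition), 16.1.5 (SAEs) and 16.1.7 (AEs leading to death) are separate outputs, with no link to the eC-SSRS counts.

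**Step 4: time windows.** The eC-SSRS post-baseline period in SAP 16.6.1 ends at Week 27/Visit 9. The Week 31 contact in protocol 11.5.12 collects AEs but no eC-SSRS. Events in those last weeks can appear only in the AE outputs.

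**Step 5: scale.** Suppose one subject in an arm has an event the table does not count. Percentage = 100 × x/n. The exact 95% limits are the 0.025 quantile of Beta(x, n−x+1) and the 0.975 quantile of Beta(x+1, n−x), with the lower limit 0 when x = 0. The SAP plans no intervals for this table; they are given only to show how little separates 0 from 1.

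| Arm size and source | Shown, x = 0 | With the event, x = 1 |
|---|---|---|
| 50 (SAP 3.1) | 0.0% (0 to 7.11%) | 2.0% (0.05 to 10.65%) |
| 93 (protocol 7.1, Arm 1) | 0.0% (0 to 3.89%) | 1.08% (0.03 to 5.85%) |
| 97 (protocol 7.1, Arm 2) | 0.0% (0 to 3.73%) | 1.03% (0.03 to 5.61%) |

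The SAP and protocol differ on enrollment, so both sets of arm sizes are shown.

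**The case against.** The strongest reply is that the endpoint is self-report by design. A table of subjects' answers that omits investigator-reported events is what the endpoint promises, and feeding in AE records changes it. This holds for attempts. Assigning an AE-reported attempt to Category 9 would bypass the scale's distinction between actual, interrupted and aborted attempts. It does not rescue Category 10: a purely self-reported table has no place for a category that nobody can self-report.

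A reader might also infer that suicides and attempts are lost to the study, or that any attempt not followed by a fully completed form disappears. The documents do not support either reading:
- Serious and fatal events appear in the SAE tables, the summary of AEs leading to death, the listing of deaths and disposition.
- An incomplete eC-SSRS record is tabulated when the visit has no complete one, so a yes on a partial form counts.
- The form is scheduled at every site visit from Visit 1 to Visit 9 and at the Early Discontinuation Visit, and unscheduled visits count post-baseline. A non-fatal attempt is missed only if no later eC-SSRS record carries the yes.
- A subject with an earlier qualifying yes stays in the composites.

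Two further replies are fair. Since Category 10 is empty, the four-category and five-category composites give the same numbers, so that mismatch alone changes no result. And the eligibility criteria exclude a suicide attempt within two years, recent active plan or intent, and a recent major depressive episode, while all summaries are descriptive.

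**Conclusion.** The point stands, within the eC-SSRS tables only. Category 10 has no possible source under the written rule, so its row is zero by construction, and a suicide would be miscounted in the composites unless the subject had already answered yes to another item. No passage in either document supplies a different source. This rests on the text of the SAP and protocol; a form or data specification outside them could say more.

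The practical size is small. The documents give no expected rate of suicidal events, and a very low one is assumed here. The 2.0-point figure (1/50) is what one event would be worth and should not be read as an expected bias. No test or arm comparison depends on it. The change should still be made: the rule would give a wrong count in exactly the case the row exists to report, and it is better settled before database lock than after an event is known.

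**What to change.** In SAP 16.6.1, choose one of two routes:

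1. Derive Category 10 for the overall post-baseline period from the Adverse Events source (fatal outcome with a suicide preferred term), include it in both composites, and footnote the source and the time window. Disposition alone is not enough, because it lists death as a reason without its cause.
2. Remove Category 10, define the composites on Categories 6-9 and 1-9, and cross-refer to the table of AEs leading to death.

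Under either route, reconcile the four behavior sub-categories in protocol 11.3.7.1 with the five in the SAP. Do not recode AE-reported attempts as Category 9. Add a footnote that attempts known only from AE or SAE records, including those after the last eC-SSRS form, are shown in the AE and SAE tables.

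The cost is one rule or one deletion plus footnotes, using data already collected. The downside of route 1 is one table row that draws on a second, footnoted source. Under route 2, the suicidality table no longer reports suicides itself.

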16. Subject has a major medical illness other than epilepsy that would prevent safe participation in this study, at the discretion of the Investigator, including (but not limited to) cardiac disease, thyroid disease, hepatic or renal impairment, endocrine or metabolic disease, gastrointestinal disease, or hematologic disease. Note: Active medical conditions that are minor or well-controlled are not exclusionary if they do not affect risk to the subject or the study results. If the effect of the condition in regard to the risk to the subject or to the study results is unclear, the Medical Monitor should be consulted.
17. Subjects with clinically relevant laboratory abnormalities at screening (eg, sodium < 130 mEq/L, alanine transaminase (ALT) or aspartate transaminase (AST) > 2.0 times the upper limit of the normal, white blood cell [WBC] count $< 3,000$ cells/mm 3 , estimated creatinine clearance < 50 mL/min, or has values for thyroid testing (free triiodothyronine (T3), free thyroxine (T4), thyroid stimulating hormone [TSH]) indicating the presence of significant thyroid dysfunction.
18. Subject has a history or presence of abnormal electrocardiogram (ECG), which in the Investigator's opinion is clinically significant or QT interval corrected for heart rate using the Fridericia method (QTcF) of ≥ 450 msec per screening ECG.

19. Subject has second- or third-degree atrioventricular block that is not corrected with a pacemaker.
20. Subjects who meet the Diagnostic and Statistical Manual of Mental Disorders, 5th edition text revision defined criteria for major depressive episode within the last 6 months. Subjects with mild, chronic depression without recent hospitalization who are being maintained on a stable dose of a single antidepressant are acceptable.
21. Subject has an active suicidal plan or intent (in the Investigator's opinion) in the past 4 weeks prior to screening.
22. Subject has a history of suicide attempt in the last 2 years prior to screening.
23. Subject has other major psychiatric disorders.
24. Subjects who are not able to complete the diaries in the Investigator's opinion.
25. Subject has a history of alcohol or substance abuse within 2 years prior to screening for study participation, or subjects currently using alcohol, drugs of abuse, or any prescribed or over-the-counter medication in a manner, which, in the opinion of the Investigator, indicates abuse.

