6.3. Baseline

For the seizure-related endpoints, baseline will be defined as the seizure data for the longest available period up to 3 months prior to screening from seizure history and from screening to first dose of study medication from the paper seizure diary.

Hence, the period of baseline will be calculated as the days of (1 month, 2 months or 3 months) + the number of days from Screening to the first dose from paper seizure dairy. One month will be calculated as 30.42 days.

For all other endpoints, baseline will be defined as the last non-missing measurement taken prior to the first dose of study drug.

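### The eC-SSRS shift tables start from the worst lifetime score, so ideation that rises above a subject's recent state but not above the lifetime maximum is tabulated as no change or a downward shift

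*SAP*

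**What the plan says.** The eC-SSRS has its own baseline table in SAP 16.6.1. The baseline row combines the screening version, described as "Baseline/Screening – life time, past one months and past two years", with the Since Last Visit record at Visit 2. The derivation rule is "Most severe outcome". The post-baseline row takes the most severe outcome over the on-treatment visits to Week 27, all from the Since Last Visit version.

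The ideation score at any time point "is defined as the maximum suicidal ideation category (1-5) present for the time of interest", with 0 if there is none. A score of 4 or 5 is called serious. The comparison is then specified: "Shift in suicidal ideation score from baseline to the post-baseline time point", and also to individual visits. The visits listed are Visits 3 to 9 and the early discontinuation visit.

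The same section plans counts of subjects with any ideation and with each subtype at baseline, post-baseline and each scheduled visit. Visit 2 has its own entry, and screening is shown on the lifetime recall. No count of subjects whose ideation emerged or worsened on treatment is defined.

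For endpoints other than seizures, SAP 6.3 says that "baseline will be defined as the last non-missing measurement taken prior to the first dose of study drug". Protocol 15.3 has the same rule.

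Eligibility is restricted by recency. Exclusion 21 reads "Subject has an active suicidal plan or intent (in the Investigator's opinion) in the past 4 weeks prior to screening". Exclusion 22 covers attempts in the last 2 years, and exclusion 20 a major depressive episode in the last 6 months. None of them excludes ideation that lies further back.

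**The concern.** A shift table is read as change from the state in which a subject started treatment. Here the starting state is a maximum over a lifetime, and it is set against a maximum over about 26 weeks, or over the 2 to 4 weeks between visits in the by-visit tables. In a subject whose worst ideation is years old, the starting score is well above the state at first dose. Recurrence on treatment then looks like stability or a fall.

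The entry rules make such subjects possible, because they exclude recent severe states and admit older history. The stake is how a safety table is read. The study is open-label, every subject receives ESL and the two arms are not compared, so within-subject change carries much of the interpretation. Safety is a secondary objective, and the eC-SSRS is a named safety endpoint.

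**Working it through.** The documents give no figure on this point to reproduce, so the check applies the stated rule to every possible score pattern.

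**Inputs (SAP 16.6.1).**
- L = baseline score under the SAP rule, the maximum over the whole recall and Visit 2, 0 to 5.
- R = recent pre-treatment score, the maximum over the past-month response and Visit 2. Both lie inside the pool that defines L, so R ≤ L always.
- P = maximum on-treatment score, 0 to 5.

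**Direction of the error.** The SAP shift is P − L and the shift from the recent state is P − R. Since R ≤ L, P − L ≤ P − R in every subject. The rule can turn a rise into no change or a fall. It cannot create a rise.

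**Examples.**

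| L | R | P | SAP shift | Shift from recent state |
|---|---|---|---|---|
| 4 | 0 | 3 | 4 to 3, down | 0 to 3, up |
| 4 | 0 | 4 | 4 to 4, none | 0 to 4, up |
| 3 | 0 | 0 | 3 to 0, down | 0 to 0, none |
| 0 | 0 | 1 | 0 to 1, up | 0 to 1, up |

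In the second row the subject reaches a score that the SAP calls serious, and the table shows no change.

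**No recent ideation, some on treatment (R = 0, P = 1 to 5).** There are 6 × 5 = 30 patterns.
- Up (P > L): 5 + 4 + 3 + 2 + 1 + 0 = 15.
- No change (P = L): 5.
- Down (P < L): 30 − 15 − 5 = 10.
- With a lifetime history (L ≥ 1) there are 5 × 5 = 25 patterns, of which 1 + 2 + 3 + 4 + 5 = 15 are no change or down.
- With L = 0, all 5 patterns show as up.

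**Any rise above the recent state (P > R).** For L = 0 to 5 there are 5 + 9 + 12 + 14 + 15 + 15 = 70 patterns.
- Up: 5 + 8 + 9 + 8 + 5 + 0 = 35.
- No change: 1 + 2 + 3 + 4 + 5 = 15.
- Down: 70 − 35 − 15 = 20.

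With R as baseline, all 70 show as up.

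**False falls.** A subject with P = R < L has not changed from the recent state but is tabulated as down. There are 1 + 2 + 3 + 4 + 5 = 15 such patterns.

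These totals count possible patterns, each once. They are not expected proportions of subjects.

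**The case against.** Much can be said for the plan as written.

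- **The ideation is still reported.** Every on-treatment report enters the post-baseline and by-visit counts whatever the baseline, and the pre-dose Visit 2 count stands beside them. A reader might infer that ideation disappears from the report, or that nothing else compares before with after. The documents support neither. NDDI-E item 4 is also summarised as change from a last pre-dose baseline. What is missing is narrower: the counts are group totals and do not tie a subject's eC-SSRS result to that subject's recent state.
- **First-ever ideation is shown correctly.** A reader might infer that any new ideation is masked. Only recurrence at or below an earlier maximum is affected.
- **The SAP defines no improved or worsened category.** If the table is an ordinary cross-tabulation, the on-treatment score can be read from the cell. The layout templates are not in the documents. The starting score would still be the lifetime maximum in any layout.
- **The baseline is deliberate.** A reader might infer a breach of SAP 6.3. Section 16.6.1 gives an explicit definition for this instrument, and a specific rule qualifies a general one. The fair remark is that 6.3 does not mention the exception and 3.4.2 does not list it as a change from the protocol.
- **The protocol endpoint is untouched.** It is the percentage of subjects in each class. The shift is an SAP addition, and no testing is planned.

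These points stand. They limit the matter to the shift tables and do not alter how those tables behave.

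**Conclusion.** The point holds for the shift tables, and it is a cheap improvement; it does not invalidate any planned output. The only within-subject eC-SSRS comparison in the plan is tilted one way. In subjects with a lifetime history, a rise above the recent state up to the lifetime maximum is tabulated as no change or down, and remote history alone yields a downward shift.

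The number of subjects cannot be stated. A reader might assume that 20–30% of about 100 subjects have lifetime ideation and infer that emergent ideation in 20 to 30 subjects would be masked. The documents give no such prevalence. That count would also require every one of those subjects to have no recent ideation, to develop it on treatment and to stay at or below the earlier maximum. The only firm ceiling is the number with lifetime ideation, which the planned screening count will show. Nor do the documents say that these subjects are at higher risk than others.

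The conclusion rests on the baseline row being read as one pooled maximum, as its text indicates.

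**What to change.** In SAP 16.6.1:

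1. Add a shift table against a recent baseline, defined as the worse of the past-month screening response and the Visit 2 Since Last Visit response.
2. Add the number and percentage of subjects, by arm, whose maximum on-treatment ideation score exceeds that recent baseline.
3. Keep the present shift as a second table, with lifetime baseline in its title.
4. State in SAP 6.3 that the eC-SSRS uses its own baseline.

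The cost is SAP wording, a repeat of an existing table and one added count. The SAP lists the past-month recall as part of baseline; the protocol calls the screening version lifetime, so confirm that the past-month response is stored separately.

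The recent baseline has a limit of its own. Taking a month as about 30 days, plus the 7 to 17 days between screening and Visit 2, it covers 37 to 47 days, or 5 to 7 weeks, against about 26 weeks on treatment. The longer window has more opportunity to record ideation, so the overall post-baseline shift will lean toward upward shifts. The two tables should be read together.
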